4.3. Demographic data collection

At baseline, socio-demographic data will be collected from participants at the initial in-person interview. The collected variables will be:

- Age
- Gender
- Sex
- City of origin
- City of residence (to know urbanisation and migration)
- Formal Education Level
- Employment/occupation status
- Digital literacy and Digital Health literacy²⁸
- Height
- Weight

4.4. Effectiveness data collection

Effectiveness measurement time points will be at baseline and after 12 weeks.

Among secondary outcome measures to assess the iBeChange intervention effectiveness compared to the control group (described in Table 3), one main secondary measure has been selected per health habit or psychosocial measure according to those behaviours or symptoms with most evidence of cancer risk. These are the following:

- Smoking: Number of smoked cigarettes per day
- Body Weight: Body mass index calculation
- Alcohol: Weekly alcohol consumption
- Nutrition: Intake of processed food and red meat per week
- Physical activity: Minutes of moderate to vigorous physical activity per week
- Psychosocial: PSS-4 score for perceived stress.

4.4.1. iBeChange questionnaire on Cancer Nutritional factors

After a thorough literature review, there were some extensively used nutrition questionnaires assessing for adherence to the Mediterranean diet. However, this is not the scope of this pilot study: we aim to specifically assess the nutritional groups associated with increased or decreased risk of cancer. No validated scale assessing these specific constructs was found. Therefore, the iBeChange consortium is developing an iBeChange questionnaire on Cancer Nutritional factors. Questions will be selected and validated through experts' panels in an iterative manner. A paper-

format protocol detailing the development and validation of the scale will be attached to this pilot protocol submission for IRB approval.

4.5. Cost-effectiveness data collection

Cost-effectiveness measurement time points for the pilot study will be at baseline and after 12 weeks.

To evaluate the cost-effectiveness, variables such as household income, living situation, healthcare costs, medication, and diagnostic tests will be asked from participants. Sections B, C, H, D and F from the modular PECUNIA Resource Use Measurement (PECUNIA RUM) were selected to assess the cost-effectiveness of the iBeChange intervention compared to standard clinical practice. These target the following areas:

- Section B: Non-residential health and social care (7-13 items)
- **Section C**: Medication (2 items)
- Section H: Out-of-pocket and other expenses (4 items)
- Section D: Unpaid help (informal care) (1 item)
- **Section F**: Employment and productivity (1-5 items).

Additionally, the EQ-5D-5L questionnaire will assess quality of life at the same time points.

4.6. Wearable data collection

Through the Oura ring device, data related to Physical activity and psychosocial health will be collected. The specific variables collected per each group are the following:

Physical activity: number of steps; metabolic equivalent of the task (MET) (1-minute intervals); average MET minutes (average MET level sustained throughout the day, factoring in all activities and rest periods); high activity MET minutes and High activity time; low activity MET minutes and low activity time; medium activity MET minutes and medium activity time; sedentary MET minutes and sedentary time; inactivity alerts; active calories (calories burned during physical activity); total calories (total number of calories burned during the day).

Psychosocial health:

Sleep data: heart rate; heart rate variability; latency (time it takes to fall asleep from the moment the subject gets into bed); temperature deviation; restless period; average breath; efficiency (ratio of time actually spent sleeping to the total time spent in bed); sleep score; light, deep and REM sleep time; readiness score (body's recovery status and physical preparedness); start-end bed time.

Stress Resilience: daytime stress (in terms of heart rate, heart rate variability, motion and temperature throughout the day)

4.7. Future usability and human-computer interaction studies

Besides the satisfaction and usability measures collected in this pilot study of the use of the iBeChange app and of the Oura smart rings, additional studies will be conducted at the University of Palermo (UNIPA) to further investigate the acceptance, usability, and human-computer

interaction of the iBeChange mobile application. Each of these will be the subject of a dedicated research protocol to be submitted for approval to UNIPA's Institutional Review Board.

These studies will aim to provide deeper insights into user experience and engagement with the app and the wearable devices. They will focus on assessing the usability and acceptance of the application, human-machine interaction, including engagement and potential challenges in user interaction with the system. Both studies will examine key features such as integration with wearable devices and the voice recording function.

The UNIPA team, in collaboration with other partners within the iBeChange consortium, will define the objectives, methodologies, and procedures for both studies. Each study will involve a sample of at least 20-25 users, selected according to inclusion criteria similar to those established for the pilot study and the RCT. Participants will use the application for several weeks, during which their interactions with the system will be monitored. All participants recruited in these studies will be assigned an Oura ring for data collection.

At the end of the study periods, a mixed-methods approach will be employed to assess user experience. This will include semi-structured interviews or focus groups, self-report measures, and behavioural analysis tools such as eye tracking. By combining qualitative and quantitative data, these studies will provide a comprehensive understanding of usage patterns and the effectiveness of different app features.

5. Study Population

5.1. Inclusion and Exclusion criteria

Table 4. Inclusion and Exclusion criteria for the iBeChange Pilot Study

	✓ IC1. Ability to understand and voluntarily provide signed written informed consent approved by the study site's Institutional Review Board (IRB).
Inclusion criteria	✓ IC2. Being at a high-risk age for breast (women between 45-70), colorectal (individuals between 50-70) or lung cancer (individuals aged 50-80 years).
	✓ IC3. Having participated in a test for early detection of cancer (i.e., mammography or ultrasound for breast cancer, faecal occult blood test (FOBT) or colonoscopy for colorectal cancer, and CT-scan for lung cancer).
	- EC1. History of any prior or current personal cancer diagnosis. In the case of colorectal and breast cancer, this will be restricted to the pathology tested for screening.
Exclusion criteria	- EC2. Current severe disease that may significantly compromise the performance on the study according to the criteria of the investigator.
	- EC3. Not owning a smartphone.
	 EC4. For breast and colorectal cancer, participants undergoing screening for alert symptoms or family history of these cancer types (the latest are eligible for specific hereditary cancer programs).

Regarding EC2, the term "severe disease" is broadly defined to include conditions that would prevent participants from fully engaging in the study's activities. The criteria remain intentionally broad to allow flexibility in assessing potential participants. Specific examples may be refined as cases arise during the pilot study. Examples of excluded conditions:

Physical disabilities such as blindness or deafness, particularly in cases where the technology (e.g., mobile applications) is not adapted for these impairments, are examples of conditions that would prevent participation.

Participants with severe mental illness or cognitive impairments that hinder their ability to understand and navigate the app will be excluded from the study. Severe mental illness will not automatically lead to exclusion; instead, such cases will be referred to general practitioners for appropriate care.

As for EC3, there is no feasible solution for providing smartphones to those without them due to logistical and financial constraints. Past studies attempted to loan devices, but it was not possible in this case.

Even though it may be challenging to address this issue in the current study, the team acknowledges it as a limitation. The percentage of excluded people is expected to decrease by the time the study is completed, but it remains an unavoidable problem.

Wearable sub-study

Participants to be enrolled in the wearable sub-study must fulfil the following additional criteria detailed in Table 5.

Table 5. Inclusion and Exclusion criteria for the iBeChange Wearable Sub-study

Inclusion criteria	 ✓ ICW1. Ability to understand and voluntarily provide signed written informed consent for the wearable sub-study approved by the study site's Institutional Review Board (IRB). ✓ ICW2. Being allocated by randomisation in the Experimental group of the iBeChange pilot study.
Exclusion criteria	 ECW1. History of any prior or current skin problems, such as allergic skin reactions, active eczema, or contagious skin conditions personal cancer diagnosis (restricted to the pathology tested for screening). ECW2. Known allergies or previous reaction to titanium or medical-grade plastic.

5.2. Strategies for recruitment and retention

Three recruitment centres are participating in iBeChange. These are:

Table 6. Recruitment centres: characteristics and expected recruitment size for the iBeChange Pilot Study

Centre	City, Country	Ownership	Funding Type	Type of entity	N per cancer type (expected)
Institut Català d'Oncologia (ICO)	Hospitalet del Llobregat, Spain	Public	Catalan Health Service (CatSalut)	Hospital and comprehensive cancer centre integrated into the Catalan public health system	Breast = 20 Colorectal = 40
Istituto Europeo di Oncologia (IEO)	Milano, Italy	Private, Non- Profit	Private funding, with agreements for public healthcare services	Hospital and comprehensive cancer centre that collaborates with the Italian National Health Service for some publicly funded treatments	Lung = 10 Breast = 50
University of Medicine and Pharmacy Carol Davila (UMFCD)	Bucuresti, Romania	Public	Publicly funded as a state university hospital	General hospital ascribed to public university receiving funding through the Romanian Ministry of Education and Ministry of Health	Breast = 20 Colorectal = 40

Given their different nature, the recruitment strategy will be slightly different in each recruitment centre:

ICO, Spain (breast and colorectal)

Breast cancer:

Participants at ICO are recruited through the breast cancer screening program. Through a postal letter, women at **50-70** years old are invited to the program. Only those women attending a mammography test at ICO's radiology service are suitable for participation. Mammography technicians provide a brochure with a Quick Response (QR) code/phone to contact to chat.

Participants access a webpage with basic study information, where they can either directly contact the study personnel or provide their contact details and consent to be contacted. If they agree, participants will be contacted by telephone by a researcher to provide more information. If inclusion/exclusion criteria and willingness to participate are confirmed, then an in-person appointment for ICF signature is scheduled.

Colorectal cancer:

Participants at ICO are recruited through the colorectal cancer screening program. Through a postal letter, individuals at **50-70** years old are invited to the program. Only those individuals returning a faecal occult blood test (FOBT) sample to the pharmacies are suitable for participation. Pharmacies' personnel provide a brochure with a QR code/phone to contact to chat.

Participants access a webpage with basic study information, where they can either directly contact the study personnel or provide their contact details and consent to be contacted. If they agree, participants will be contacted by telephone by a researcher to provide more information. If inclusion/exclusion criteria and willingness to participate are confirmed, then an in-person appointment for ICF signature is scheduled.

IEO, Italy (breast and lung):

Breast cancer:

At IEO, women **aged 45-69** years old can participate in breast cancer screening by voluntarily booking, both privately and via national health care system. They are contacted by phone call to be introduced to the iBeChange study.

Interested people will receive via email an informative brochure with a study overview and a link directing to the project's website.

Signed informed consent will be collected at the cancer screening test appointment.

Lung cancer:

At IEO, individuals **aged 50-80** years with no clear signs of lung cancer (e.g., worsening cough, haemoptysis, unexplained weight loss) who are current smokers or former smokers that quit less than 15 years ago are eligible to participate in lung cancer screening by voluntarily booking if they have smoked at least (a) 10 cigarettes per day for 30 years, (b) 15 cigarettes per day for 25 years, or (c) 20 cigarettes per day for 20 years (> 20 packs/year). Individuals with history of cancer in the past 5 years are excluded. Since lung cancer screening is not usually available at IEO and is not offered by the Italian health care system, an *ad hoc* lung cancer screening program will be organised and promoted for this pilot study. Eligible participants will be able to access the screening with no additional costs. They are contacted by phone call to be introduced to the iBeChange study.

Interested people will receive via email an informative brochure with a study overview and a link directing to the project's website.

Signed informed consent will be collected at the cancer screening test appointment.

UMFCD, Romania (breast and colorectal):

Breast cancer:

Participants at UMFCD are recruited through general practitioners (GPs). At a GP visit, if inclusion/exclusion criteria and willingness to participate are confirmed, women **50-70** years old can be sent for screening in specialised centres (external, different centres, public or private). Only those women attending a mammography or an ultrasound test are suitable for participation. If inclusion/exclusion criteria and willingness to participate are confirmed, an in-person appointment for ICF signature is scheduled.

Colorectal cancer:

Participants at UMFCD are recruited through general practitioners (GPs). At a GP visit, if inclusion/exclusion criteria and willingness to participate are confirmed, individuals 50-70 years old can be sent for screening in specialised centres (external, different centres, public or private). Only those individuals attending a FOBT or a colonoscopy are suitable for participation. If inclusion/exclusion criteria and willingness to participate are confirmed, an in-person appointment for ICF signature is scheduled.

Common:

After ICF signature, participants are centrally randomised through REDCap, ²⁹ and, if assigned to the experimental group (EG), the iBeChange app is downloaded together with a step-by-step demonstration on its functionalities by the researcher.

If assigned to the iBeChange group, the participant is asked for their willingness to use the study wearable. If yes, a specific ICF for wearables is signed and the participant is randomised to receive or not the wearable. If assigned to the wearable sub-group, and the needed size is available, the Oura smart ring is delivered (EGw).

The step-by-step demonstration of iBeChange will be detailed in a standardised protocol for welcoming and introducing the app to participants across all centres, considering age and other factors.

For enrolled participants of all groups, questionnaires will be sent by email through the REDCap platform. These will include demographic variables as well as questionnaires for assessing primary and secondary outcomes. These questionnaires are designed for the participant to answer at home, not in the recruitment centre.

Intervention for the iBeChange participants will start as soon as they provide enough information in the app for it to recommend a health pillar and deliver personalised interventions. For further details, please visit section 6.2.

Participants will also be asked for optional consent of voice recordings to analyse potential vocal stress markers. This will be registered and the option to record within the iBeChange app will only be displayed to those participants in the experimental group that have consented.

Regarding wearables, the ICF signature appointment and the introduction to the iBeChange app will also be used to deliver the device. The consumer-grade Oura ring has been selected. A stock of devices will be available at each recruitment centre. An Oura ring of the participant's size will be delivered and connected to the participant's iBeChange app account.

In case the needed size is not available at one centre, it will be requested at the other sites, and that participant will be excluded from the wearable sub-study so as not to delay the start of the intervention delivery.

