2.1. Synopsis

Table 1. iBeChange Pilot Study Synopsis

[figure not shown]
Title:	Behavioural change for cancer prevention: A pilot study protocol of a digital intervention		
Grant Number:	Horizon Mission Cancer HORIZON-MISS-2023-CANCER-01 ID: 101136840		
Study Description:	This pilot study will assess the feasibility of iBeChange, a digital platform designed to promote personalised behavioural change to address lifestyle and psychosocial risk factors associated with cancer risk. Twelve weeks of iBeChange intervention will be compared to treatment as usual, consisting of receiving general cancer prevention guidelines. A sub-group of participants in the iBeChange intervention group will receive an Oura ring wearable device to automatically and unobtrusively collect physiological data.		
Objectives*:	The primary objective of this pilot study is to assess the feasibility of iBeChange in real-life settings.		
	Additionally, preliminary data regarding the effectiveness and cost-effectiveness of iBeChange compared to general cancer prevention guidelines will be collected.		
	Also, exploratory data from Oura smart rings will be collected from the allocated participants.		
	Finally, usability and satisfaction will be assessed for the iBeChange platform and for the selected wearable devices.		
Endpoints*:	The primary endpoints are the feasibility of the recruitment, data collection, and ability to manage and implement the study and intervention.		
	The secondary endpoints are the effectiveness and cost-effectiveness of iBeChange in achieving a sustainable behavioural change in Smoking, Alcohol consumption, Nutrition, Physical activity habits, and Emotional Wellbeing symptoms.		
Study Population:	This pilot study will enrol a total of 180 healthy individuals (60 per clinical centre), both men and women, aged 45-80 who undergo screening tests for breast, colorectal or lung cancer, from Spain, Italy and Romania.		
Phase * or Stage:	Not Applicable (Behavioural Intervention)		
Description of Sites/Facilities Enrolling Participants:	This pilot study is a European multicentric trial. It will be conducted in the centres: Institut Català d'Oncologia (ICO, Barcelona, Spain), Istituto Euro di Oncologia (IEO, Milano, Italy), and Universitatea de Medicina si Farm Carol Davila (UMFCD, Bucarest, Romania).		

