7.2. Data Processing Particulars and Data Flow Diagrams

7.2.1. Participant Recruitment and Studies Management Stage

[figure not shown]
Please refer to Figure 5 below. The starting point for the data flows is contained within the Participant Recruitment and Study Management Phase and commences when the Health Care Professional (HCP) at each of the recruitment centres (ICO, IEO and UMFCD) approaches a patient during routine care/cancer screening and asks whether they would like to Participate in the iBeChange Study. The Patient will either consent as per steps 0C or decline as per steps 0D. On declining, that patient will no longer engage with iBeChange. Note that the steps listed in this section refer to each of the participating centres (ICO, IEO and UMFCD).

On consenting, the patient will become a Participant and will be randomised to be part of the Control Group at steps OCC or the Experimental Group at steps OCE. If randomised to the Experimental Group, Participants will be asked if they agree to being part of the wearables study, at which point they will be further randomised under steps 0CW to see if they form part of the Wearables sub-study. At steps 0CV, participants will also be asked if they consent to doing voice recordings for the voice recordings analysis and have the risks involved with this explained to them as part of the consenting process. These steps are also represented in the iBeChange pilot study diagram in Figure 1.

Their HCP will register each participant under the steps 1HCR according to the Group they are randomised to and whether they will form part of the Wearables sub-study and whether they have consented to voice analysis. The information will be gathered locally via the REDCap System available at each site and hosted by ICO as per steps 1HCR. The REDCap system has several functions where one is for HCPs to complete information entry.

Figure 5. Data Flow Diagram: Data processing for the iBeChange pilot study (next page)

Deliverable 5.1 iBeChange pilot study protocol

IBeCHANGE ID: 101136840

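### At UMFCD, screening referral is written as conditional on willingness to join, which leaves decliners' screening unstated and can inflate the recruitment rate

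*Protocol*

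**What the plan says.** Protocol section 5.2 describes UMFCD recruitment through general practitioners, with one paragraph for each cancer type. For colorectal screening: "At a GP visit, if inclusion/exclusion criteria and willingness to participate are confirmed, individuals 50-70 years old can be sent for screening". The breast paragraph opens with the same two conditions and continues: "women 50-70 years old can be sent for screening in specialised centres (external, different centres, public or private". Attendance at the test is then required. For colorectal: "Only those individuals attending a FOBT or a colonoscopy are suitable for participation"; the breast paragraph asks for a mammography or ultrasound. Criteria and willingness are then confirmed a second time, and a consent appointment is booked.

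Section 5.1 (Table 4) sets the relevant inclusion criterion: "IC3. Having participated in a test for early detection of cancer".

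On people who decline, section 7.2.1 says only that their contact with iBeChange ends. It does not mention their screening.

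Section 8.1 sets the recruitment feasibility threshold at 50% of eligible patients consenting. Section 8.4 plans to analyse that proportion.

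The test has a different origin at the other centres (section 5.2). ICO recruits people who attend an existing programme. IEO breast entrants book their own screening. IEO lung entrants use a programme set up for the pilot.

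**The concern.** Two things are at stake.

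The first is what the text commits the site to. Read literally, a person at a UMFCD general practice is asked about the trial first and is sent for a screening test if willing. The protocol is going to ethics committees, and they would see a screening referral tied to agreeing to join a trial of a behavioural app. The order appears in both paragraphs, so it is unlikely to be a single slip.

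The second is a primary feasibility result. IC3 makes having been tested part of eligibility. If willingness is asked before the test, people who say no are not sent along this route and need never become eligible. People who say yes but do not attend the external test are also lost before consent and before they meet IC3. Whoever reaches the eligible group has already been filtered for willingness. The proportion of eligible people who consent then means something different at UMFCD from what it means at ICO, where eligibility follows attendance at a programme that exists apart from the study.

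**Working it through.** **1. The planned sample (section 5.2, Table 6).** ICO 20 + 40 = 60. IEO 10 + 50 = 60. UMFCD ("Breast = 20 Colorectal = 40") 20 + 40 = 60. The total is 180, which matches the synopsis and section 8.2 (10% of 2 × 900 = 180).

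**2. UMFCD share.** 60/180 = 33.3% (colorectal 40/180 = 22.2%, breast 20/180 = 11.1%).

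**3. Share whose screening was prompted by the trial.** The protocol does not say how many UMFCD entrants would have been referred anyway, so only bounds can be given.
- All would have been referred anyway: 0/180 = 0%.
- None would have been: 60/180 = 33.3%.
- Adding the 10 IEO lung entrants, whose programme is expressly created for the pilot, the whole-trial range is 10/180 = 5.6% to 70/180 = 38.9%.

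**4. Order of steps at UMFCD against IC3.**

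| Step in section 5.2 | Can IC3 be met by someone not yet tested? |
|---|---|
| GP visit: criteria and willingness confirmed | No |
| Sent to an external centre | No |
| Test attended | Yes, from here |
| Criteria and willingness confirmed again | Yes |
| Consent appointment | Yes |

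The first check cannot cover IC3 for such a person. The second can, and it comes before consent.

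**5. Possible effect on the recruitment rate.** This is an illustration. Assume the same true willingness w at all three centres, no other losses, and 60 enrolled per centre. Each centre then asks 60/w people and has 60(1 − w)/w decliners. Let f be the fraction of UMFCD decliners missing from the denominator.

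Reported overall rate = 180 / [120/w + 60 + (1 − f) × 60(1 − w)/w]

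Take w = 40%, borrowed from the 60% refusal rate that section 8.2 assumes for the full RCT. Each centre asks 60/0.40 = 150 and has 90 decliners.
- f = 0: 180/(300 + 60 + 90) = 180/450 = 40.0%, below the threshold.
- f = 0.5: 180/(300 + 60 + 45) = 180/405 = 44.4%.
- f = 1: 180/(300 + 60) = 180/360 = 50.0%, at the threshold.

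Take w = 50%, the protocol's own threshold. Each centre asks 120 and has 60 decliners.
- f = 0: 180/360 = 50.0%.
- f = 1: 180/(240 + 60) = 60.0%.

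With f = 1 the formula reduces to 3w/(2 + w). This reaches 50% when 3w = 1 + 0.5w, that is w = 0.40. In this worst case, any true rate from 40% to just under 50% would be reported as meeting the threshold. UMFCD's own rate would be 60/60 = 100% whatever w is.

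Willing people who do not attend the test act in the same direction. If a fraction a attend, the number asked at UMFCD is 60/(w × a), and those who do not attend are also outside the eligible group. The protocol gives no value for a.

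**The case against.** Much of the case on the other side stands.

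- The verb in the referral sentence is permissive, and the section describes how participants are recruited. A reader might infer that decliners are refused screening. The protocol does not say so; it is silent.
- A reader might infer that a third of the sample are people screened because of the trial. That is only the upper bound, and the documents do not describe usual referral practice in Romania.
- A reader might infer that people could be randomised without meeting IC3. They could not: the second check comes after the test and before consent. Someone tested earlier could even meet IC3 at the GP visit.
- The synopsis and section 7.2.1 might seem to contradict section 5.2. They do not. The synopsis speaks of people "who undergo screening tests for breast, colorectal or lung cancer, from Spain, Italy and Romania", which fits UMFCD entrants and fixes no order. Section 7.2.1 says the professional "approaches a patient during routine care/cancer screening and asks whether they would like to Participate in the iBeChange Study", and a GP visit is routine care.
- Raising the study before the test is not peculiar to UMFCD. IEO contacts people by phone and takes consent at the screening appointment.
- The comparison of randomised groups is not biased by this. Randomisation is stratified by centre and screening type (section 6.5), and the models account for site (section 8.5).
- The 60% refusal rate is a planning figure for the RCT, not a measured rate at the GP stage. Recruitment logs may also be specified in documents not shown.

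The written condition itself is not answered. Willingness precedes referral in both paragraphs, no text covers the decliner's screening, and the recruitment metric is defined on eligible people although eligibility comes after the willingness filter. A site that follows the text would produce the problem even if the wording is only loose.

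**Conclusion.** The point holds in a limited form and should be corrected. As written, referral for screening at UMFCD is conditional on willingness to join, and what happens to a decliner's screening is not stated. The conflict with IC3 is confined to the first eligibility check.

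The passages concern 60 of 180 planned participants. Between 0% and 33.3% of the sample may be UMFCD entrants whose screening was prompted by the trial, and the documents cannot narrow that range.

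The statistical consequence falls on the primary recruitment result rather than on the comparison between arms. The size of the inflation depends on true willingness, on test attendance and on how many decliners go uncounted, none of which the protocol gives. Under the stated assumptions, a true 40% could be reported as anything from 40% to 50%, which is enough to change the conclusion against the threshold.

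**What to change.** Reconcile sections 5.1 (IC3) and 5.2 (both UMFCD paragraphs), and state whether referral for screening depends on willingness to join and what applies to a person who declines. The clinical pathway itself is for the protocol team to decide. Make clear which criteria are checked at the GP visit and which after the test.

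At UMFCD, log the numbers asked at the GP visit, willing, referred, tested, eligible and consented. Report the recruitment rate of sections 8.1 and 8.4 with people who decline at the GP visit kept in the denominator, and show willing people who did not attend the test as a separate loss.

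The cost is a rewording of two paragraphs and a short log kept by GPs or site staff. The recruitment rate may look less favourable.
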